2. LIST OF ABBREVIATIONS

Abbreviation	Definition
ABC/MBC	advanced/metastatic breast cancer
AE	adverse events
AEM	adverse events monitoring
AI	aromatase inhibitor
ANOVA	analysis of variance
ATC	anatomical therapeutic chemical
BMI	body mass index
CDK	cyclin-dependent kinase
CDK4/6-I	cyclin-dependent kinase 4 and 6 inhibitors
CI	confidence internal
CIOMS	council for international organizations of medical sciences
CKD	chronic kidney disease
COPD	chronic obstructive pulmonary disease
CPT	current procedural terminology
CRF	case report form
CVD	cardiovascular disease
DCT	data collection tool
ECOG	Eastern Cooperative Oncology Group
ER+	Estrogen receptor positive
FDA	food and drug administration
gBRCAm	germline breast cancer gene mutation
GIS	geographic information systems
HER2	human epidermal growth factor receptor 2
HER2-	human epidermal growth factor receptor 2 negative
HMO	health maintenance organization
HR	hormone receptor
HR+	hormone receptor positive
ICD-9	international classification of diseases ,ninth revision
IEC	independent ethics committee
IQR	interquartile range
IRB	international review board
ISPOR	international society for pharmacoeconomics and outcomes research
K-M	kaplan-meier (curve)
MHS	Maccabi Healthcare Services
N	number
NIS	non-interventional study
CCI	CCI

PDF	portable document format
PR+	progesterone receptor positive
RWE	real-world evidence
SD	standard deviation
SES	socioeconomic status
TTNT	time to next treatment
USA	united states of america
YRR	your reporting responsibilities

4. AMENDMENTS AND UPDATES

5. MILESTONES

Milestone	Planned date
Start of data collection	08 November 2020
End of data collection	30 June 2022
Final study report	31 December 2022

6. RATIONALE AND BACKGROUND

Breast cancer is a major cause of mortality in females worldwide. Hormone receptor positive (HR+) and human epidermal growth factor receptor 2 negative (HER2-) breast cancer is the most commonly diagnosed subtype accounting for around 75% of all diagnosed breast cancers¹. Palbociclib is a first in class cyclin-dependent kinase 4 and 6 (CDK4/6) inhibitor that has been approved for use in HR+/HER2- advanced/ metastatic breast cancer (ABC/ MBC) patients in a number of indications on the basis of efficacy demonstrated in 3 pivotal clinical trials; PALOMA-1 and PALOMA 2 (initial endocrine-based therapy) and PALOMA-3 (after progression following endocrine therapy) ^{2,3}. As a result of the recent approvals there is a need to understand the real world usage and clinical outcomes of patients receiving CDK4/6 inhibitors, including palbociclib, in order to inform future treatment decisions.

There is high level of screening and awareness for breast cancer in Israel. Palbociclib was included in the national health basket and therefore reimbursed since January 2018 in all lines of treatment, according to the labeling.

Although there is Real-World Evidence (RWE) on palbociclib published from the USA, Argentina, Germany and Italy ^{4,5,6} there is no awareness of RWE with palbociclib coming from Israel.

7. RESEARCH QUESTION AND OBJECTIVES

Primary Objective: To describe patient demographics, clinical characteristics, clinical outcomes and treatment patterns of adult breast cancer patients who have initiated palbociclib combination treatment as per the national basket of health services in January 2018 until August 2020 for all lines of therapy. Extended follow up for treatment patterns to 30th June 2022.

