8. RESEARCH METHODS

8.1. Study design

This is a population based retrospective database study that will include patients with metastatic, HR+/ HER2- breast cancer and who initiated first or subsequent lines of treatment with palbociclib. Data will be available from Maccabi Healthcare Services (MHS) database in Israel for patients who received approval for treatment with palbociclib since 01 January 2018 until 31 August 2020.

Treatment amendment and extension: Treatment lines will be rerun for the same patient cohort for an additional year and a half of follow-up to 30 June 2022.

The database review followed by a medical record review will capture data from approximately 500-700 patients on demographics, clinical characteristics, disease history, treatment history, palbociclib dosing, clinical outcomes and post-palbociclib combination therapy treatment data. The study will be descriptive in nature therefore no control or comparator groups will be included.

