8.2. Setting

Patients (age \geq 18 years) will be identified from MHS purchase data between 01 July 2017 until 31 August 2020.

Index date will be defined as date of initiation of palbociclib treatment.

Patient records must meet the following criteria to be eligible for the medical record reviews. Patients must be at least 18 years of age at index date and they must have been diagnosed with HR+/HER2- ABC/ MBC. Patients must have received palbociclib combination in line with Israel approved indications. A minimum of 6 months follow up of palbociclib combination therapy prior to date of medical record review will be necessary for inclusion. This will permit the capture of meaningful clinical outcomes data. Patients will be followed through the end of the observation period, date of death or left the health maintenance organization (HMO).

A full list of the inclusion criteria can be found in Section 9.2.1.

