- Number (N) (%) patients receiving first, second- and third-line treatments by drug name and therapeutic group, median duration of each line of therapy, and number of cycles for each line of therapy. Treatment lines are defined according to the sequence of dispensed medications, with information captured both from pharmacy database (for medications approved by the HMO), and from hospital medical records (including information on medications provided by private insurance and clinical studies) using the following algorithm. Any drug purchased within 1 month of a new line is considered part of that line. Cessation of a drug from a combination regimen is considered the same line as the patient is not receiving additional treatment. Cessation is likely due to tolerance issues or adverse effects although we do not know the reason as our data is from purchase data. Addition of a new drug to a current regimen is considered a new treatment line.
- Index treatment regimen - palbociclib combination partner: Aromatase Inhibitors (AI) or fulvestrant; Subsequent therapy per lines of therapy.
- Dosing and dose changes, interruptions, delays, and discontinuations associated with palbociclib therapy.
- Treatment lines will be rerun for extended follow up to 30 June 2022.

8.3.4. Cancer related variables:

These variables will be extracted from patient PDF files/ letters sent to MHS from the physician.

- Date of initial breast cancer diagnosis.
- Histology.
- Location of metastases: bones, brain, visceral, lymph nodes, other.

- ECOG performance status at diagnosis.
- Molecular status data: performed HER2/ HR tests (yes/no).
- Hormone sensitivity: primary or secondary resistance.
- Progression of disease from imaging.

8.3.5. Clinical outcomes for palbociclib (analysed separately by therapy line):

- N (%) progression at 6, 12 and 24 months.
- Duration of treatment on palbociclib (Median time on treatment).
- Time on treatment for subsequent line of therapy.
- Time to chemotherapy after palbociclib treatment.

■ CCI [REDACTED]

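### The extension to 30 June 2022 is written for treatment patterns only, the cut-off for clinical outcomes is not stated, and 24-month progression is a crude percentage with no denominator or censoring rule

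*Combined protocol and SAP*

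**What the plan says.** **Entry.** Three sections give the entry window. Section 7 refers to the "national basket of health services in January 2018 until August 2020 for all lines of therapy". Section 8.1 takes patients with "approval for treatment with palbociclib since 01 January 2018 until 31 August 2020". Section 8.2 has patients "identified from MHS purchase data between 01 July 2017 until 31 August 2020". Section 8.5 expects 500 to 700 patients.

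**Extension.** Section 7 names clinical outcomes and treatment patterns as separate parts of the objective and then adds "Extended follow up for treatment patterns to 30th June 2022". Section 8.1 says "Treatment lines will be rerun for the same patient cohort for an additional year and a half of follow-up to 30 June 2022". Section 8.3.3 (treatment patterns) repeats this for treatment lines. Section 8.3.5 has no such sentence.

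**End of follow-up.** Section 5 gives a single end of data collection, 30 June 2022, for the whole study. Sections 8.2, 8.3 and 8.7 refer to the end of observation or of the study without a date.

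**Minimum follow-up.** Section 8.2 requires "A minimum of 6 months follow up of palbociclib combination therapy prior to date of medical record review", and that review has no date. Inclusion criterion 3 in section 8.2.1 instead asks for six months of available palbociclib treatment data.

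**Outcomes.** Section 8.3.5 lists "N (%) progression at 6, 12 and 24 months", duration of treatment on palbociclib, time on the subsequent line, and time to chemotherapy. The table in section 8.3 classes time to next treatment (TTNT) as a treatment characteristic, but time to chemotherapy and post-palbociclib duration as clinical outcomes. All three have structured data as their source. Section 8.6 says that imaging response, discontinuation and some chemotherapy come from chart review of letters.

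**The concern.** Closely related quantities fall on different sides of the extension. The median duration of each line (8.3.3) is extended. Duration on palbociclib (8.3.5), which for the palbociclib line measures much the same thing, is not mentioned. TTNT and time to chemotherapy share landmarks at 6, 12, 18 and 24 months but carry different labels, so a programmer following the text could give them different follow-up. The report could then contain two durations for one line, and late landmarks that rest on early starters although later purchase data are already being pulled.

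Progression raises a further problem. Entry is staggered over at least 32 months, so a count and percentage at 24 months depends on what is done with patients not yet followed that long. Keeping them in the denominator as non-progressed understates progression. Dropping them unless they have already progressed overstates it. The visible text does not choose.

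**Working it through.** **1. Implied earlier cut.** Section 8.1 gives the length and end of the extension: 30 June 2022 minus 18 months is the end of December 2020. No date in the plan confirms this. Counting to 30 June 2022 from the last index date (31 August 2020) gives 22 months, and from the start of data collection (8 November 2020, section 5) about 20 months. December 2020 is therefore an inference.

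**2. Range of potential follow-up**, index dates 1 January 2018 to 31 August 2020: 4 to 36 months at 31 December 2020, and 22 to 54 months at 30 June 2022.

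**3. Share able to be observed for 24 months from index.** The plan gives no accrual pattern, so uniform daily starts are assumed. Share = (days from window start to the last start date that allows 24 full months) / (days in window). Death and leaving the health plan are ignored.

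| Window | Cut | Can reach 24 months | Cannot |
|---|---|---|---|
| Jan 2018–Aug 2020 (974 days) | 31 Dec 2020 | 366/974 = 37.6% | 62.4% (312 of 500; 437 of 700) |
| Jul 2017–Aug 2020 (1,158 days) | 31 Dec 2020 | 550/1,158 = 47.5% | 52.5% (263 of 500; 368 of 700) |
| Jan 2018–Aug 2020 | 30 Jun 2022 | 913/974 = 93.7% | 6.3% (31 of 500; 44 of 700) |
| Jul 2017–Aug 2020 | 30 Jun 2022 | 1,097/1,158 = 94.7% | 5.3% (26 of 500; 37 of 700) |

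**4. Sensitivity to accrual.** Let the monthly start rate in 2018 be r times the rate in the other 20 months of the January 2018 window. The share that can reach 24 months at 31 December 2020 is 12r/(12r + 20).
- r = 0.5: 23.1% can, 76.9% cannot.
- r = 1: 37.5% can, 62.5% cannot.
- r = 20/12 = 1.67: 50% each.
- r = 2: 54.5% can, 45.5% cannot.

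**5. Time to chemotherapy.** Its clock starts at the end of index treatment (8.3 table), so the shares in step 3 do not apply to it. As an illustration, assume six months on palbociclib. The 24-month landmark then needs 30 months from index. Under uniform starts over 32 months, (36 − 30)/32 = 19% can reach it at December 2020, and (54 − 30)/32 = 75% at June 2022.

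**6. Six-month minimum.** At 31 December 2020, starters from 2 July to 31 August 2020 lack six months: 61/974 = 6.3% (31 of 500; 44 of 700). This conflicts with criterion 3 only if data end in December 2020. Under section 8.2 the period runs back from the record review. A start on 31 August 2020 completes six months on 28 February 2021, within the collection period in section 5, so a review on or after that date admits every starter.

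**The case against.** A reader might infer that clinical outcomes are frozen at December 2020, that most patients therefore cannot reach 24 months, and that July–August 2020 starters cannot qualify. The documents do not support any of these as fact. No section sets a December 2020 cut for clinical outcomes, and the milestones fit a later one. Whether it is most patients depends on accrual. Reimbursement began in January 2018, so front-loaded starts are possible, but no monthly counts are given. The late starters qualify under section 8.2 if the review is late enough.

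It is also fair to say that time on palbociclib, subsequent-line time and, in part, time to chemotherapy derive from treatment lines, so the rerun may be meant to update them. Kaplan–Meier estimation, specified for TTNT and time to chemotherapy, handles staggered entry; for those outcomes an early cut costs precision and consistency and does not in itself cause bias. A structured-data rerun adds no follow-up to chart-based progression or to chemotherapy known only from letters, and not repeating chart review is a legitimate choice in a descriptive study. Finally, one outcome is blacked out in 8.3 and 8.3.5, and the sentence in 8.7 on plots is interrupted, so part of the outcome handling cannot be seen.

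All of this stands. It does not supply a cut-off for each outcome, a review date, or a denominator for the progression line, which is fully visible.

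**Conclusion.** The point holds as a gap between the stated extension and the outcomes listed in 8.3.5. If June 2022 applies to all outcomes, sections 7, 8.1 and 8.3.3 are worded too narrowly. If December 2020 applies to clinical outcomes, related durations come from different cuts and 24-month results lose many patients. In that second case the loss is about 62% under uniform starts from January 2018, 52.5% from July 2017, and under half if 2018 starts ran above 1.67 times the later rate, against 5% to 6% at June 2022. These shares rest on the inferred cut and on assumed accrual, and they apply to clocks that start at index.

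The risk of bias lies mainly in the crude progression percentages, and it remains whichever cut is used if chart follow-up ends earlier than the cut. Its size cannot be given, because the documents contain no progression rate and no review dates. The six-month conflict is conditional and affects about 6% of patients.

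**What to change.** 1. State 30 June 2022 as the single data cut for all outcomes derived from purchase or other structured data: time on palbociclib, subsequent-line duration, TTNT, time to chemotherapy and death. Reconcile sections 5, 7, 8.1, 8.2, 8.3.3 and 8.3.5 with it, and give the date or dates of the record review.
2. Replace the crude progression percentages with a time-to-event estimate that censors each patient at the last reviewed letter or imaging, and show numbers at risk at 6, 12 and 24 months. Section 8.7 already derives time from initiation to progression, so no new variable is needed. Where chemotherapy known only from letters counts as an event, censor in the same way, because absence from purchase data after the last letter does not show that none was given.
3. Express the six-month requirement as potential follow-up from index date to the data cut, and reconcile section 8.2 with criterion 3 in 8.2.1. At 30 June 2022 the last starter has 22 months, so every patient meets it.

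The cost is wording and a rerun of existing programs on structured data already being extended. Progression at 24 months will stay imprecise unless chart review is also updated; this fix does not require that.

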8. RESEARCH METHODS

8.1. Study design

This is a population based retrospective database study that will include patients with metastatic, HR+/ HER2- breast cancer and who initiated first or subsequent lines of treatment with palbociclib. Data will be available from Maccabi Healthcare Services (MHS) database in Israel for patients who received approval for treatment with palbociclib since 01 January 2018 until 31 August 2020.

Treatment amendment and extension: Treatment lines will be rerun for the same patient cohort for an additional year and a half of follow-up to 30 June 2022.

The database review followed by a medical record review will capture data from approximately 500-700 patients on demographics, clinical characteristics, disease history, treatment history, palbociclib dosing, clinical outcomes and post-palbociclib combination therapy treatment data. The study will be descriptive in nature therefore no control or comparator groups will be included.

8.2. Setting

Patients (age \geq 18 years) will be identified from MHS purchase data between 01 July 2017 until 31 August 2020.

Index date will be defined as date of initiation of palbociclib treatment.

Patient records must meet the following criteria to be eligible for the medical record reviews. Patients must be at least 18 years of age at index date and they must have been diagnosed with HR+/HER2- ABC/ MBC. Patients must have received palbociclib combination in line with Israel approved indications. A minimum of 6 months follow up of palbociclib combination therapy prior to date of medical record review will be necessary for inclusion. This will permit the capture of meaningful clinical outcomes data. Patients will be followed through the end of the observation period, date of death or left the health maintenance organization (HMO).

A full list of the inclusion criteria can be found in Section 9.2.1.

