8.2.1. Inclusion criteria

Patients must meet all of the following inclusion criteria to be eligible for inclusion in the study:

1. A diagnosis of metastatic breast cancer, based on the National/MHS cancer registry.
2. Newly diagnosed metastatic breast cancer patients and newly treated with palbociclib within 6 months of diagnosis, in any line of treatment in the metastatic setting.
3. Available data on palbociclib treatment for at least 6 months.
4. Continuous healthcare plan enrolment in MHS for at least one year before index date.
5. At least 18 years of age at index date.

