Genetic testing for gBRCAm performed	MHS structured data	Baseline characteristic	Baseline	Reported	yes/no
Death	MHS structured data	Endpoint	After index date		Death is captured from National Insurance Data
Disease Characteristics					
Date of initial breast cancer diagnosis	National cancer registry	Baseline characteristic	Baseline	Reported	Records may be incomplete
Histology	Extracted from PDF patient data files	Baseline characteristic	Baseline	Reported	
Location of metastases	Extracted from PDF patient data files	Baseline characteristic	Baseline	Reported	Bone, brain, lymph nodes, ovary, visceral
Visceral/non visceral status	Extracted from PDF patient data files	Baseline characteristic	Baseline	Reported	Non-visceral, visceral (lungs, liver), bone only
Eastern Cooperative Oncology Group (ECOG) performance status at diagnosis	Extracted from PDF patient data files	Baseline characteristic	Baseline	Reported	Grouped as 0-1, 2, 3-4, unknown/missing
Molecular status data: performed HER2/ HR tests	Extracted from PDF patient data files	Baseline characteristic	Baseline	Reported	yes/no
Hormone sensitivity	Extracted from PDF patient data files	Baseline characteristic	Baseline	Reported	primary or secondary resistance
Variable	Source	Role in study	Period of measurement	Reporting phase	Operational definition
Progression of disease from imaging	Extracted from PDF patient data files	Baseline characteristic	Baseline	Reported	
Treatment Characteristics					

Index treatment regimen	MHS structured data	Treatment characteristic	Study observation period	Reported	Palbociclib combination treatment - combination with aromatase inhibitor or fulvestrant.
Lines of therapy	MHS structured data and PDF patient data files.	Treatment characteristic	Study observation period	Reported	Identified according to the sequence of dispensed medications.
Median duration of each line of therapy	MHS structured data	Treatment characteristic	Study observation period	Reported	Duration in weeks or months between the start and stop of each line of therapy will be reported as mean (SD) and median (IQR)
Number of cycles of index treatment	MHS structured data	Treatment characteristic	Study observation period	Reported	Mean (SD) and Median (IQR)
Index palbociclib treatment dose	MHS structured data	Treatment characteristic	Study observation period	Reported	Mean (SD) and Median (IQR)

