Index palbociclib treatment dose schedule change	MHS structured data	Treatment characteristic	Study observation period	Reported	Proportion of patients with dose changes
Date of treatment initiation	MHS structured data	Treatment characteristic	Study observation period	Not Reported	First date will be used if a regimen consists of more than one drug given on different dates.
Index treatment end date	MHS structured data	Treatment characteristic	Study observation period	Not Reported	Date of final treatment for each drug or regimen. It is possible that the patient's treatment stop date is not documented if the patient dies, is lost to follow up or is still on therapy. The final treatment date death date or end of

					study date will be used, whichever is earliest.
Variable	Source	Role in study	Period of measurement	Reporting phase	Operational definition
Post-palbociclib treatment duration	MHS structured data	Clinical Outcomes	Study observation period	Not Reported	
The regimen received by patients following discontinuation from the palbociclib treatment.
 
The duration (in weeks) between the start and stop of the post-palbociclib treatment. Findings will be summarized as the mean (\pm SD) and median (range) of values.

					subsequent treatment for unknown reasons
Time to chemotherapy after palbociclib treatment	MHS structured data	Clinical Outcomes	Study observation period	Reported	Time to chemotherapy (Kaplan Meier method median (95% CI)) from end of index treatment and start of chemotherapy. Summary of number of events and censored patients at 6, 12, 18, 24 months.
Time to next treatment (TTNT)	MHS structured data	Treatment characteristic	Study observation period	Reported	TTNT will be defined as the interval (in weeks or months) between the start of the index treatment date and the date of the next-line treatment. Patients who did not advance to the next treatment will be censored on the study end date or death, whichever occurs first. Kaplan-Meier (K-M) method with 95% CI and summary tables of

					events and censored patients at 6, 12, 18, 24 months.
CCI					

8.3.1. Demographic characteristics at baseline (from structured electronic database):

- Patient demographics: age, age group and gender.
- Region of residence (North, Central, South).

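### The palbociclib start date is taken from MHS structured data alone, although the plan reads hospital records for privately funded and trial supply, so a patient with earlier non-HMO palbociclib can be indexed late and counted as newly treated

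*Combined protocol and SAP*

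**What the plan says.** Section 8.2 finds adults through dispensing: they "will be identified from MHS purchase data between 01 July 2017 until 31 August 2020". It then states: "Index date will be defined as date of initiation of palbociclib treatment".

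In the Section 8.3 variables table, the row "Date of treatment initiation" names MHS structured data as its only source and is marked as not reported. Its one rule covers regimens whose drugs start on different dates. The row for lines of therapy has a wider source: "MHS structured data and PDF patient data files". Section 8.3.3 gives the reason: the pharmacy database covers medications that the HMO approved, and further information comes "from hospital medical records (including information on medications provided by private insurance and clinical studies". Section 8.6 takes systemic therapy other than chemotherapy from the main database.

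On who may enter, Section 8.2.1 criterion 2 asks for patients "newly treated with palbociclib within 6 months of diagnosis, in any line of treatment in the metastatic setting". Criterion 4 asks for one year of MHS enrolment before index. The only exclusion in Section 8.2.2 is use of HER2 inhibitors. On funding, Section 6 says: "Palbociclib was included in the national health basket and therefore reimbursed since January 2018 in all lines of treatment".

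**The concern.** The plan recognises that some drug supply lies outside the HMO pharmacy data and allows for it when numbering lines, but not when setting time zero. If a patient took palbociclib privately or in a study before the first MHS purchase, the stated source returns the later date.

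Much hangs on that date. TTNT and time on treatment run from it. The percentages on treatment at 3, 6, 12 and 24 months (Annex 1, table 3), the cycle count, the index dose and the 3-month co-medication look-back also depend on it. The treatment-patterns table counts reductions from 125 mg, and one made before the first MHS purchase would not show in purchase data. The line algorithm, which does read hospital records, could place the index date in the middle of a line.

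Eligibility can go wrong both ways. Someone who was not newly treated, or who did not start under the national basket as Section 7 requires, could be admitted. Someone who truly started within 6 months of diagnosis could fail criterion 2 because the first MHS purchase came later. Since the initiation date is not reported, a reader of the results could not detect either error.

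**Working it through.** The plan has no figure to reproduce: Section 8.5 gives an expected 500-700 patients without a sample-size calculation. The check has two parts.

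**1. Sources compared**

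| Item | Source named | Section |
|---|---|---|
| Finding patients | MHS purchase data | 8.2 |
| Date of treatment initiation | MHS structured data | 8.3 |
| Lines of therapy | MHS structured data and PDF files | 8.3, 8.3.3 |
| Private or study supply | Hospital medical records | 8.3.3 |

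No other rule closes the gap. Criterion 2 names no look-back source or washout. Criterion 4 requires an enrolled year, not a palbociclib-free year. Prior palbociclib is not an exclusion. The purchase window opens on 01 July 2017, 184 days before 01 January 2018, but it looks back only in purchase data. Section 8.9 promises uniform handling of conflicting data without saying which date prevails.

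If criterion 2 is applied to the recorded date and counted from metastatic diagnosis, the true and recorded starts both lie within 6 months of that diagnosis, so the hidden delay in the metastatic setting is at most about 6 months. The phrase about any line of treatment leaves that reading uncertain.

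**2. Size of the effect (illustration)**

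The documents give neither the share affected, f, nor the delay, d. Both are assumed, as are the true median m (12-24 months) and the Weibull shape k (0.8 falling hazard, 1 constant, 1.3 rising).

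- True curve: S(t) = exp[-ln 2 × (t/m)^k].
- A late-indexed patient is seen only if still on drug at d, so that group's curve is S(t+d)/S(d).
- Cohort curve: (1-f)·S(t) + f·S(t+d)/S(d), solved for 0.5.
- Median of the affected group alone: (m^k + d^k)^(1/k) - d.

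For m = 18 and d = 6, the affected group's median is:
- k = 0.8: (10.10 + 4.19)^1.25 - 6 = 21.8 months
- k = 1: (18 + 6) - 6 = 18.0 months
- k = 1.3: (42.84 + 10.27)^(1/1.3) - 6 = 15.2 months

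Cohort median in months, d = 6:

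| True median | f | k = 0.8 | k = 1 | k = 1.3 |
|---|---|---|---|---|
| 12 | 20% | 12.62 | 12.00 | 11.52 |
| 18 | 10% | 18.37 | 18.00 | 17.72 |
| 18 | 20% | 18.75 | 18.00 | 17.45 |
| 24 | 5% | 24.21 | 24.00 | 23.85 |
| 24 | 20% | 24.85 | 24.00 | 23.40 |

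The largest shifts are +0.85 (24.85 - 24) and -0.60 (23.40 - 24) months. Of 500-700 patients, f = 5%, 10% and 20% mean 25-35, 50-70 and 100-140 patients.

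**The case against.** The strongest reply is that the plan defines the index date as initiation, not as first purchase; purchases only find the patients. Criterion 2 and the objective in Section 7 already intend new starters under the basket, and the chart review captures treatment history and palbociclib dosing, so earlier use should come to light. Section 8.4 describes full pharmacy prescription and purchase data, the purchase window opens before reimbursement, and Section 8.3.3 does not literally say that private supply is found only in hospital records.

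Part of this stands. The intent is a new-user cohort, and no passage shows that any patient received palbociclib outside the HMO. But the only source named for the date omits the records that could show it, and nothing says what to do when chart and purchase disagree.

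A reader might go further and infer a large group of prevalent users, for example everyone indexed in January-June 2018: 6/32 entry months = 18.75%, or 94-131 of 500-700 under uniform accrual. The documents do not support this. It requires private supply to continue for months after reimbursement began. With an equally assumed crossover of 1-2 months, the group is 1/32 to 2/32 of accrual, or 16-44 patients, and only an unknown fraction of them would have had earlier supply.

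A reader might also infer that early stopping is understated or time on treatment biased in a known direction. Late indexing removes months from the clock but also selects patients who stayed on drug. These effects oppose each other and cancel under a constant hazard. If criterion 3 means six months on drug, early stoppers are lost across the whole cohort, which is a separate matter.

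**Conclusion.** The source mismatch is in the text, and no other rule corrects it. Followed as written, the plan would misdate any patient with earlier non-HMO palbociclib and could misjudge that patient's eligibility. The number is unknown and may be small or zero. The effect on median time on treatment is modest: within about 0.9 months for up to 20% affected, delays up to 6 months, true medians of 12-24 months and Weibull shapes of 0.8-1.3, with undetermined sign. The main harm is to patient-level dating, starting dose, early dose changes and eligibility. Treatment patterns are part of the primary objective of this descriptive study, so that is reason enough to correct it. The documents do not establish that prevalent users are actually present.

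**What to change.** 1. In Section 8.3, give the initiation date the same two sources as the row for lines of therapy: MHS structured data and the PDF patient files.
2. In Section 8.2, define the index date as the earliest palbociclib date in either source.
3. Apply criterion 2, the 01 January 2018 to 31 August 2020 initiation window, baseline, and every time-to-event clock to that date. Section 7 frames the window as initiation and Section 8.1 as treatment approval, so say explicitly that it governs initiation.
4. Exclude from the main analysis patients whose earliest date falls outside the window, as not having initiated under the national basket.
5. Report how many patients were re-dated and how many were excluded.

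Patients re-dated within the window were still found only because they reached an MHS purchase, so their time before it is free of discontinuation by selection. If there are more than a few, a sensitivity analysis with delayed entry at first purchase would show whether this matters.

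The cost is one date field in a chart abstraction already planned, a few sentences of text, and possibly a few fewer patients.
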